10.3 Clinical laboratory evaluations

Laboratory values, including markedly abnormal laboratory values will be presented descriptively by treatment group for the SS, MS, and AMS.

The markedly abnormal tables and those based on common terminology criteria for AEs (CTCAE) grade will be produced only for selected laboratory variables.

For tables where data are summarized by visit, unscheduled and repeat visits will not be summarized, but these data will be included in listings. For tables where multiple measurements over a period of time are considered (as in shift tables), unscheduled and repeat visits will be considered as long as they were collected in the period being summarized (values observed more than 140 days after the last administration of study medication are not considered). All summaries will be presented in SI units and will be based on observed case values. In the case where laboratory values are below the LLQ, then these will be set to the midpoint between 0 and the lower limit of quantification for the purpose of summarizing the data. The following summaries are required:

- A summary of the absolute and change from Baseline values in each laboratory variable by treatment group and visit**

- A summary of the number and percentage of participants experiencing markedly abnormal values at any time while on treatment (assessment on or following the first dose of study treatment through the minimum of period of interest (Week 16) or date of last dose + 140 days) by laboratory variable and treatment group. Two separate tables will show results for the Initial Treatment Period (for the SS) and the Initial and Maintenance Treatment Period (for the AMS).
- A summary of the number and percentage of participants with a given CTCAE grade (0,1,2,3, or 4) based on minimum/maximum post-baseline value by laboratory variable and treatment group. Two separate tables will show results for the Initial Treatment Period (for the SS) and the Initial and Maintenance Treatment Period (for the AMS).
- A shift table of the number and percentage of participants experiencing CTCAE grade 0,1,2,3, or 4 values (as applicable) at Baseline to maximum post-Baseline CTCAE grade, by laboratory variable and treatment group. Two separate tables will show results for the Initial Treatment Period (for the SS) and the Initial and Maintenance Treatment Period (for the AMS).

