- A by-participant listing of all laboratory data (including urinalysis) will be provided. This listing will be presented by treatment group and will include: center, participant identifier, age, sex, race, weight, visit, laboratory variable, result (with abnormal values flagged as “L” or “H” accordingly) and unit.

Markedly abnormal values are defined as those with a severity of Grade 3 and above based on the CTCAE criteria Version 4.03. Definitions of markedly abnormal values using the Grade 3 cut points are given in the tables below for age ranges of ≥ 17 years [Table 10-4](#) for markedly abnormal liver function test values, [Table 10-5](#) for markedly abnormal biochemistry values and [Table 10-6](#) for markedly abnormal hematology values). Tables summarizing markedly abnormal values will include a summary (counts and percentages) of markedly abnormal labs observed at any time while on treatment (ie, treatment-emergent markedly abnormal [TEMA]). For this summary, Baseline values and values observed more than 140 days after the last administration of study medication are not considered. The laboratory results classified as Grade 3 or Grade 4 will be summarized and listed separately.

Table 10-4: Definitions of Markedly Abnormal Liver Function Values

Parameter name	Conventional		Standard		Abnormal Designation
	Unit	Criteria	Unit	Criteria	
ALP	U/L	$>5.0 \times \text{ULN}$	U/L	$>5.0 \times \text{ULN}$	AH
ALT	U/L	$>5.0 \times \text{ULN}$	U/L	$>5.0 \times \text{ULN}$	AH
AST	U/L	$>5.0 \times \text{ULN}$	U/L	$>5.0 \times \text{ULN}$	AH
Total Bilirubin	mg/dL	$>3.0 \times \text{ULN}$	umol/L	$>3.0 \times \text{ULN}$	AH
GGT	U/L	$>5.0 \times \text{ULN}$	U/L	$>5.0 \times \text{ULN}$	AH

Table 10–5: Definitions of Markedly Abnormal Biochemistry Values

Parameter name	Conventional		Standard		Abnormal Designation
	Unit	Criteria	Unit	Criteria	
Creatinine ¹	mg/dL	> 3.0 x Baseline or >3.0 x ULN	umol/L	> 3.0 x Baseline or >3.0 x ULN	AH
Glucose	mg/dL	<40 >250	mmol/L	<1.7 >13.9	AL AH
Calcium	mg/dL	>12.5 <7.0	mmol/L	>3.1 <1.75	AH AL
Magnesium	mg/dL	>3.0 <0.9	mmol/L	>1.23 <0.4	AH AL
Potassium	mmol/L	>6.0 <3.0	mmol/L	>6.0 <3.0	AH AL
Sodium	mmol/L	>155 <130	mmol/L	>155 <130	AH AL
Cholesterol	mg/dL	>400	mmol/L	>10.34	AH

1 The markedly abnormal definitions for creatinine are based on the logical or, if either criterion is met the creatinine value will be designated as abnormal high.

Table 10–6: Definitions of Markedly Abnormal Hematology Values

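### Table 10-5 gives two different limits for markedly low glucose: below 40 mg/dL is below about 2.2 mmol/L, but the SI column says below 1.7 mmol/L

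*SAP*

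**What the plan says.** SAP Section 10.3 fixes what counts as markedly abnormal: "Markedly abnormal values are defined as those with a severity of Grade 3 and above based on the CTCAE criteria Version 4.03". It then points to Tables 10-4 to 10-6: "Definitions of markedly abnormal values using the Grade 3 cut points are given in the tables below". Each table has a conventional-unit column and a standard-unit column for the same designation, AL for low and AH for high. The glucose row of Table 10-5 reads "Glucose mg/dL <40 >250 mmol/L <1.7 >13.9 AL AH".

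On units, the same section states: "All summaries will be presented in SI units and will be based on observed case values".

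The limits feed counts and percentages of participants with markedly abnormal values, in one table for the Initial Treatment Period (Safety Set) and one for the combined Initial and Maintenance Treatment Period (Active Medication Set). Section 10.3 also requires by-visit summaries of absolute values and changes, and a by-participant listing of all laboratory data with L or H flags. Table 12-1, which sets out CTCAE grades for biochemistry, has no glucose row.

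**The concern.** One cut point written in two unit systems should be the same concentration in both. In the glucose row the high limits agree with each other and the low limits do not. At least one of the two low-limit cells is therefore wrong, and the current text contains no other glucose limit that would settle which.

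At stake is the number of participants counted as markedly low in the TEMA tables. Two programmers who both follow the SAP, one applying the conventional column and the other the standard column, could report different counts. The SI rule makes the standard column the natural choice, and that is the column with the lower limit, so the likely direction is towards fewer participants counted.

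**Working it through.** **Inputs**, all from the glucose row of Table 10-5:
- Low: 40 mg/dL paired with 1.7 mmol/L.
- High: 250 mg/dL paired with 13.9 mmol/L.

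**Step 1. Conversion factor from the high pair.** 250 / 13.9 = 17.99 mg/dL per mmol/L. As an outside check, the molar mass of glucose (about 180.16 g/mol) gives 18.02, and 250 / 18.02 = 13.87 mmol/L, so the stated 13.9 is reproduced.

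**Step 2. Low limit on the same factor.**
- 40 / 17.99 = 2.22 mmol/L; the table says 1.7.
- 1.7 × 17.99 = 30.6 mg/dL; the table says 40.

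**Step 3. Can rounding explain it?**
- If 13.9 stands for anything from 13.85 to 13.95, then 40 mg/dL lies between 40 × 13.85 / 250 = 2.216 and 40 × 13.95 / 250 = 2.232 mmol/L.
- If 1.7 stands for anything from 1.65 to 1.75, it lies between 29.7 and 31.5 mg/dL.
- The ranges do not come near each other, so rounding does not explain it.

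**Step 4. Size of the gap.** 40 − 30.6 = 9.4 mg/dL, or 2.22 − 1.7 = 0.52 mmol/L. The SI limit is 9.4 / 40 = 23.5% below the conventional one. The results on which the two columns disagree run from 1.7 mmol/L (not itself below 1.7) to just under 2.22 mmol/L, about 31 to just under 40 mg/dL.

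**Step 5. Is the table loose in general?** Analytes with both a high and a low pair allow an internal check, because the two pairs should imply the same factor.

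| Analyte | Factor from high pair | Factor from low pair |
|---|---|---|
| Calcium | 12.5 / 3.1 = 4.03 | 7.0 / 1.75 = 4.00 |
| Magnesium | 3.0 / 1.23 = 2.44 | 0.9 / 0.4 = 2.25 |
| Glucose | 250 / 13.9 = 17.99 | 40 / 1.7 = 23.53 |

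Calcium agrees. Magnesium agrees only because its low SI limit is given to one decimal: 0.9 / 2.44 = 0.37, which rounds to 0.4. Cholesterol (400 mg/dL against 10.34 mmol/L) agrees with the standard conversion to within 0.1%, and the hemoglobin limits in Table 10-6 convert exactly. Low glucose is the only pair that fails beyond rounding.

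**Step 6. Is it current text?** Yes. The row stands in Section 10.3 itself. The log for SAP Amendment 1 shows the same pair, so the mismatch has been carried forward, and a text-extraction fault is unlikely.

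**The case against.** The arithmetic is hard to dispute. The case on the other side is about how much follows from it.

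First, the output is descriptive. No hypothesis test, alpha level, power figure or analysis set depends on the limit. Glucose is not among the safety topics of interest in Section 10.2.3, and the secondary safety endpoints in Section 2.2.3.1 are adverse-event endpoints. This stands, and it keeps the point below a must-fix.

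Second, a reader might infer that low glucose values between the two limits would go unflagged altogether. The documents do not support that. The by-participant listing carries every laboratory result, including unscheduled ones, and its L/H flag is not tied to Table 10-5. By-visit summaries include the minimum (Section 3.1), though only for scheduled visits. What is at risk is the markedly low classification and its count.

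Third, a reader might take it as settled that flags come from the SI column. The SAP requires summaries to be presented in SI units but never says which column drives the flag. SI is the natural reading, not a stated rule. The contradiction exists either way, but the direction of its effect depends on this.

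Fourth, a reader might conclude that 2.2 mmol/L is right and 1.7 is a slip, or that keeping 1.7 would break the Grade 3 statement. The documents do not show which figure was intended. The conversion shows only that the two cells disagree, and the cited CTCAE text is not reproduced for glucose anywhere in the SAP.

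**Conclusion.** The two markedly low glucose limits in Table 10-5 are different thresholds presented as one Grade 3 cut point: 40 mg/dL is about 2.2 mmol/L, and 1.7 mmol/L is about 31 mg/dL. That finding is secure and needs only the row's own high pair.

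The consequence is conditional. If the TEMA tables are programmed from the SI column, results from 1.7 to just under 2.2 mmol/L are left out of the markedly low counts. If they are programmed from the conventional column, those results are counted. This assumes that glucose is among the variables selected for the markedly abnormal tables, which its row in Table 10-5 indicates. The SAP gives no basis for estimating how many participants would have a value in that band, and the number may be small.

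The point is a should-fix for a descriptive safety table. The efficacy analyses are untouched.

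**What to change.** Before the safety tables are programmed:

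1. Look up the Grade 3 low-glucose limit in CTCAE v4.03, the version Section 10.3 cites, and reconcile both Table 10-5 cells to it, correcting whichever cell is wrong.
2. State in Section 10.3 which unit column drives the markedly abnormal flag, so that the derivation does not have to be inferred from the presentation rule.
3. Program the TEMA flag from the reconciled value.

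The cost is one table cell, one sentence and one programming constant. Doing it in advance also avoids the appearance of choosing a safety threshold after the counts have been seen.

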10.4 Vital signs, physical findings, and other observations related to safety

10.4.1 Vital signs

The following vital signs variables will be summarized: systolic blood pressure (mmHg), diastolic blood pressure (mmHg), body temperature (°C) and heart rate (beats/min). The following summaries will be provided for the SS:

- A summary of the absolute and change from Baseline value for each vital sign variable by treatment group and visit.
- A summary of the number and percentage of participants experiencing at least 1 markedly abnormal value for a vital sign variable as defined in [Table 10-7](#), by treatment group and period (Initial Treatment Period [SS], and Initial and Maintenance Treatment Period [AMS]).

Unscheduled and repeat visits will be considered as long as they were collected in the period being summarized (values observed more than 140 days after the last administration of study medication are not considered).

Table 10–7: Definitions of Markedly Abnormal Blood Pressure Values

Parameter (unit)	Markedly Abnormal Low	Markedly Abnormal High
Systolic blood pressure (mmHg)	<90 and a decrease from Baseline of ≥ 20	>180 and an increase from Baseline of ≥ 20
Diastolic blood pressure (mmHg)	<50 and a decrease from Baseline of ≥ 15	>105 and an increase from Baseline of ≥ 15

A by-participant listing of all vital signs data will be provided. This listing will be presented by treatment group and will include: center, participant identifier, age, sex, race, weight, visit, vital sign variable and result (with abnormal values flagged as “L” or “H” accordingly).

10.4.2 Electrocardiograms

Electrocardiogram data will be analyzed by treatment group and visit for the SS.

A summary of the number and percentage of participants with normal, abnormal ECG results, as determined by the central reader, will be presented for all applicable visits.

The following ECG variables will be summarized (absolute values and change from Baseline) by visit: QT corrected for heart rate using Fridericia’s formula (QTcF), RR, PR, QRS and QT.

QTc outliers are defined as QTcF values following dosing that are greater than 450 ms or are increases from Baseline greater than 30 ms. QTcF outliers will be highlighted in the data listing and summarized using the following categories:

- Values >450 ms, >480 ms, >500 ms
- Increase from Baseline of >30 ms, increase from Baseline of >60 ms, increase from Baseline of >90 ms
- Values >450 ms and increases of >30 ms. Values >500 ms and increases of >60 ms

The number and percentage of participant who meet the ECG outlier criteria at any assessment post first dose will be summarized for each period.

Two separate by-participant listing of all 12-lead ECG data will be provided based on interpretation from central reader and from site, respectively.

10.4.3 Other safety endpoints

For by-visit summaries, unscheduled and repeat visits will not be summarized, but these data will be included in listings. By-visit tables should include the SFU visit. Summaries over a period of time (as in shift tables), unscheduled and repeat visits will be considered as long as they were collected in the period being summarized (values observed more than 140 days after the last administration of study medication are not considered).

[figure not shown]
10.4.3.1 Physical examination

Abnormal results of the physical examination together with details of abnormalities: abnormality clinically significant or not, will be listed by participant and visit for SS.

[figure not shown]
10.4.3.2 Columbia-Suicide Severity Rating Scale (C-SSRS)

The eC-SSRS questionnaire will be self-administered by the study participant and assessed by trained study personnel. This scale will be used to assess SIB that may occur during the study. Results of the eC-SSRS will be summarized using the number of participants and percentage with (i) suicidal ideation, (iii) suicidal behavior, (iii) suicidal ideation or behavior, and (iv) self-injurious behavior without suicidal intent.

Suicidal ideation is defined as an event in any of the following 5 categories:

Suicidal behavior is defined as an event in any of the following 4 categories:

Suicidal behavior or ideation is defined as an event in any of the above 9 categories.

Self-injurious behavior without suicidal intent is defined as an event in the category non-suicidal self-injurious injuries.

The incidence of participants with suicidal ideation, suicidal behavior, suicidal ideation or behavior, and self-injurious behavior will be summarized for the Initial Treatment Period and the combined Initial and Maintenance Treatment Period by treatment group.

A by-participant listing of the eC-SSRS questionnaire data will be provided by treatment group.

10.4.3.3 Assessment and management of TB and TB risk factors

A summary of the number and percentage of participants with negative, positive, and indeterminate IGRA (Interferon-Gamma Release Assay) results at Screening and Week 44 will be presented.

A by-participant listing of the “Evaluation of signs and symptoms of tuberculosis” questionnaire data and IGRA results will be provided by treatment group.

By-participant listing of the result of chest x-ray for tuberculosis will be provided by treatment group.

10.4.3.4 Pregnancy testing

Pregnancy testing will consist of serum testing at the Screening. The pregnancy test will be urine at all other visits.

A by-participant listing of the pregnancy test data will be provided by treatment group.

10.4.3.5 Patient Health Questionnaire (PHQ)-9 scores

The PHQ-9 is a multipurpose instrument for screening, diagnosing, monitoring, and measuring the severity of depression. The PHQ-9 scores for depression range from 0 to 27 with higher scores indicating worse state. A score of 5 to 9 is considered to be minimal symptoms of depression. If any of the 9 questions are missing, then the score is treated as missing. A score of 10 to 14 is considered minor depression, dysthymia, or mild major depression. A score of 15 to 19 is considered to indicate moderately severe major depression, and a score ≥ 20 is considered to be severe major depression.

Change from Baseline in PHQ-9 is derived as post-Baseline score minus Baseline score.

A summary of the absolute and change from Baseline value will be presented by treatment group and visit.

The percentage of study participants with scores below 5, between 5 and 9, between 10 and 14, between 15 and 19, and greater than or equal to 20 in PHQ-9 will be summarized as a shift from Baseline by visit and treatment group based on observed values.

The percentage of study participants with scores ≥ 15 at any post-Baseline visit and the number and percentage of study participants with scores ≥ 20 at any post-Baseline visit will be summarized by treatment group based on observed values. This summary will also include the percentage of study participants with increase from baseline ≥ 5 at any post-Baseline visit.

The number and percentage of participants that complete the PHQ-9 will be calculated for each visit by treatment group. The percentage will be based on the number of participants in the RS. The summary will be repeated where the percentage is based on the subset of participants who complete each particular visit.

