3 DATA ANALYSIS CONSIDERATIONS

3.1 General presentation of summaries and analyses

Statistical analysis and generation of tables, figures, study participants data listings, and statistical output will be performed using SAS Version 9.4 or higher. All tables and listings will use Courier New font size 9.

Descriptive statistics will be displayed to provide an overview of the study results. For continuous variables, descriptive statistics will include number of study participants with available measurements (n), mean, standard deviation (SD), median, minimum, and maximum.

For PRO continuous variables, descriptive statistics will also include variable score, absolute and percentage changes from baseline, Q1 and Q3, 10th, and 90th percentiles.

If no participants have data at a given time point, then only n=0 will be presented. The other descriptive statistics will be left blank. If n < 3 then the n, minimum, and maximum only will be presented. The other descriptive statistics will be left blank. If n = 3 n, mean, median, minimum and maximum will be presented only. The other descriptive statistics will be left blank.

For categorical variables, the number and percentage of study participants in each category will be presented. Unless otherwise noted, the denominator for percentages will be based on the number of study participants included in the respective analysis set. Study participants with missing data will be accounted for using the following approaches:

- For summaries of demographics and Baseline characteristics: percentages will be based on all study participants in the analysis set and a “Missing” category (corresponding to study participants with missing data for the variable being summarized) will be included as the last row in the list of categories being summarized.
- For summaries of efficacy and safety endpoints, unless otherwise specified: percentages will be based only on those study participants with observed data for the variable being summarized. As the denominator may be different from the number of study participants in the analysis set being considered, the denominator will be displayed in the table. The general format for displaying this will be “n/Nsub (%).”

Percentages will be presented to 1 decimal place. If the percentage is 100%, a decimal will not be presented. If the count is 0, the percentage will not be presented. Typically, the % sign will be presented in the column header, but not with each individual value.

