- If Q7 is marked as "no" or "not relevant" and Q7a is missing, a score of 0 is given.
- If Q7 is missing and Q7a is missing, Q7 is considered unanswered (see below for details on how this impacts the DLQI total score).

If 1 question is left unanswered, this is scored 0 and the scores are summed and expressed as usual out of a maximum of 30. If 2 or more questions are left unanswered, the questionnaire is not scored.

Change from Baseline in DLQI total score is defined as Week 16 DLQI total score minus Baseline DLQI total score.

8.3.2.1 Primary analysis of change from Baseline in DLQI Total score at Week 16

Missing data imputation described in Section [4.2.1.2](#) will be applied.

Change from Baseline in DLQI total score will be presented by treatment group. The analysis model will be based on an ANCOVA with fixed effects of treatment, Hurley Stage at Baseline, Baseline antibiotic use and Baseline value as a covariate. The least square mean (LSM), standard error (SE), and 95% CI for the LSM will be presented by treatment group. For the comparison between placebo and bimekizumab: the difference between the LSM, the associated 97.5% CI for the contrasts, and the corresponding p-value will be presented. If one dose regimen is tested at the 0.05 significance level as determined in Section [4.5](#), then the confidence interval will be 95% instead of 97.5% for that dose with a corresponding $Z_{\alpha/2}$ of 1.96. Estimand and intercurrent event details are specified in [Table 8–2](#).

8.3.2.2 Sensitivity analysis of change from Baseline in DLQI Total score at Week 16

A sensitivity analysis using the same analysis model as in Section [8.3.2.1](#) will be used, based on observed data. Estimand and intercurrent event details are specified in [Table 8–2](#).

8.3.3 Change from Baseline in Skin Pain score at Week 16, as assessed by the “worst skin pain” item in the HSSDD

The items on the HSSDD assess patients' perception of the core symptoms of HS experienced in the past 24 hours: pain, smell or odor, drainage or oozing from HS lesions, and itch on an 11-point numeric rating scale (NRS). Two items assess skin pain: worst skin pain and average skin pain.

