10.2.1 Data considerations

Treatment-emergent AEs are defined as those AEs that have a start date on or following the first dose of study treatment through the final dose of study treatment + 140 days (covering the 20-week SFU period). If it is not possible (due to partial dates) to determine whether or not an AE is treatment-emergent then it will be assumed to be a TEAE.

An AE will be assigned to the Initial Treatment Period if it started between the first administration of IMP on Day 1 up to Week 16. An AE will be assigned to the Maintenance Treatment Period if it started between the Week 16 study drug administration and Week 48.

If an AE occurs on the date of a treatment switch, the event is attributed to the original treatment. The only exception to this is if the AE fulfills any of the criteria specified below:

- Events that fulfill the anaphylaxis criteria for acute events (refer to Appendix A in Section 12.1)
- Hypersensitivity events identified by the SMQ “Hypersensitivity (SMQ)” (see Section 12.1 Appendix A)
- Events with an high level term (HLT) of “Administration site reactions NEC”
- Events with an HLT of “Injection site reactions”

The rules for imputing partial start or stop dates are outlined in Section 4.2.4.

Any TEAEs that occur during the SFU Period will be attributed to the period in which the participant was before initiating the SFU Period.

Duration of AEs will not be calculated if there is missing stop date information.

If the intensity of an AE is unknown, it is considered as severe. If the relationship to study drug is missing, it is considered as related. Note that if the seriousness of an adverse event is unknown, every attempt should be made to resolve this prior to a snapshot for an interim analysis or database lock; in the exceptional case that the seriousness of an adverse event is still missing then no imputation should be applied for this characteristic.

Adverse events will be presented as “number of participants (percentage of participants) [number of events]”. In this style of output, “[number of events]” will include all cases of an AE including repeat occurrences in individual participants, while “number of participants” will count each participant only once.

Subject time at risk represents the time a participant is at risk for having an AE. The definitions for subject time at risk (in days) are outlined in Section 10.1. These definitions will be used for exposure-adjusted AE summaries.

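### The PHQ-9 threshold counts omit an incomplete form even when its answered items alone already reach 15 or 20

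*SAP*

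**What the plan says.** Section 10.4.3.5 of the SAP describes the scale: "The PHQ-9 scores for depression range from 0 to 27 with higher scores indicating worse state". On missing items the rule is absolute: "If any of the 9 questions are missing, then the score is treated as missing". The severity labels follow. "A score of 15 to 19 is considered to indicate moderately severe major depression", and a score of 20 or more is labelled severe.

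The section asks for mean and change summaries, a shift table by score band, and a set of threshold counts. The counts of participants at 15 or more and at 20 or more "at any post-Baseline visit will be summarized by treatment group based on observed values". A third threshold is added: "This summary will also include the percentage of study participants with increase from baseline" of 5 or more.

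The general denominator convention for safety summaries is in Section 3.1: "percentages will be based only on those study participants with observed data for the variable being summarized", unless otherwise specified. Section 10.4.3.5 specifies nothing different for the threshold counts. It contains no proration or partial-form rule, and the current Table 4-2 of imputation ranges has no PHQ-9 row.

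**The concern.** A missing total is a sensible result when the blank answer could change the classification. Here it is also applied when the blank cannot change it. If eight answered items sum to 20, the participant is at 20 or more whatever the ninth answer would have been, and the plan still records no score.

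Two things can then happen. A participant with other complete forms, all below the threshold, stays in the denominator and is reported as a non-case. A participant with no complete post-Baseline form leaves both numerator and denominator under Section 3.1. In either case the number of cases can only fall, never rise.

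PHQ-9 change is a listed safety endpoint (Section 2.2.3.2), and these counts exist to show how many participants reached a worrying level. The plan resolves other missing safety information in the cautious direction. For adverse events, "If the intensity of an AE is unknown, it is considered as severe" (Section 10.2.1), a missing relationship is taken as related, and ambiguous timing is taken as treatment-emergent (Sections 4.2.4 and 10.2.1). For the PHQ-9, an event that is already proven is left out.

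**Working it through.** The plan gives no figure for incomplete forms, so there is nothing to reproduce. The check is a bounds argument.

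**Inputs.** Nine items and a total range of 0 to 27 (Section 10.4.3.5). The item range is not stated. Equal weights give 27/9 = 3, so items run from 0 to 3. This is an inference. The thresholds are 15, 20 and an increase of 5 (same section).

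**Formula.** With *m* blank items and an answered sum *S*, the full total lies between *S* and *S* + 3*m*. It is certainly at or above a threshold *T* whenever *S* ≥ *T*. The largest possible *S* is 3 × (9 − *m*).

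| Blank items | Largest answered sum | 15 can be proven | 20 can be proven |
|---|---|---|---|
| 1 | 24 | yes | yes |
| 2 | 21 | yes | yes |
| 3 | 18 | yes | no |
| 4 | 15 | yes | no |
| 5 | 12 | no | no |

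**Examples with one blank.**
- *S* = 14: the total is 14 to 17, so 15 is not proven and missing is the right result.
- *S* = 15: the total is 15 to 18, certainly at least 15.
- *S* = 19: the total is 19 to 22, certainly at least 15, but 20 is not proven.
- *S* = 20: the total is 20 to 23, certainly at least 20.

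The plan treats all four forms alike, as missing. The same logic covers the increase. If *S* at a post-Baseline visit minus a complete Baseline total is 5 or more, the true increase is at least 5.

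**Possible size, on assumed inputs only.** Suppose 5 to 10% of participants truly reach 15 or more, and 1 to 5% of those have their only qualifying form incomplete. Expected lost cases are N × rate × share, with N from Section 2.4 (Q2W pooled for the Initial Treatment Period):
- Placebo, N = 70: 70 × 0.05 × 0.01 = 0.035 up to 70 × 0.10 × 0.05 = 0.35.
- Q2W, N = 280: 280 × 0.05 × 0.01 = 0.14 up to 280 × 0.10 × 0.05 = 1.4.

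On these assumptions the expected loss is under one participant on placebo and at most one or two on Q2W.

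**The case against.** The strongest reply is that this is a clear, reproducible complete-form rule, applied identically in every arm to a descriptive table with no test attached. It contradicts nothing else in the plan. Other instruments do tolerate blanks: for the DLQI, "If 1 question is left unanswered, this is scored 0 and the scores are summed" (Section 8.3.2), HiSQOL scores unanswered items 0 (Section 8.4.16), and each TSQM-9 domain allows one missing item (Section 8.4.23). But scoring rules are set per instrument, so that difference is not an inconsistency. This is accepted, and the point does not rest on it. What remains is that the rule gives a wrong classification for forms whose classification is already certain.

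The SAP also does not say how the PHQ-9 is captured. If a form cannot be submitted with a blank, the problem never arises. That stands, and it limits the size. So does the any-visit definition, because a participant with another complete form over the threshold is still counted.

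There is partial cover elsewhere. PHQ-9 completion is tabulated by visit and arm, Section 3.1 calls for listings of all documented data, and suicidality has its own measures (Sections 10.4.3.2 and 10.2.3.5). These lower the stakes but do not restore the threshold counts.

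Finally, a careless remedy would add a bias of its own. If partial forms counted only when they crossed, a participant with only partial forms would enter the denominator only as a case. An incomplete Baseline sum would also understate Baseline and could create false increases. Both objections are right, and the fix has to deal with them.

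**Conclusion.** The point holds in a narrow form. In the any-visit threshold counts, an incomplete form that already proves a score of at least 15 (moderately severe or worse) or at least 20 (severe) is not counted, and the participant is lost as a case unless another complete form crosses. The same applies to a proven increase of at least 5. The error runs only towards fewer cases. The conclusion needs only that no item scores below zero. The ceilings in the table also need the inferred 0 to 3 item range.

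The number affected cannot be derived from the SAP. It is likely small and may be nil.

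A reader might infer more, and the document does not support it:
- That severe cases in general disappear. The label severe applies only from 20, and many such participants would be counted from another visit.
- That blanks cluster in the most affected participants. The SAP says nothing on this.
- That one placebo participant, 1/70 = 1.4 percentage points, is the expected loss. It is only the weight of one participant; the illustration above gives less than one.
- That the whole scoring rule is wrong. A missing total is reasonable for means, changes and shifts.

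This is a minor improvement to a safety table. It has no bearing on the efficacy conclusions.

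**What to change.** Keep the missing-total rule in Section 10.4.3.5 for the mean, change and shift summaries. For the any-visit counts, add:

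- An incomplete form meets the 15 or the 20 threshold if the sum of its answered items alone reaches it.
- An incomplete post-Baseline form meets the increase of at least 5 if its answered sum minus a complete Baseline total (as defined in Section 3.3) is at least 5. Without a complete Baseline total, the increase is missing.
- The denominator is all participants with at least one post-Baseline PHQ-9 form, complete or partial. For the increase, a complete Baseline total is also required. Inclusion then does not depend on being a case.
- The number of participants with only incomplete forms is reported by arm.

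The cost is a few sentences and minor programming. Counts may rise slightly, and a participant whose only forms are partial and below the threshold is counted as not shown to cross. No complete form is reclassified, and nothing is assumed about a blank answer to call a crossing.
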